1.1. Statistical Methods

To assess the efficacy of secnidazole, we estimated failure rates and 95% exact confidence intervals for initial treatment, suppression therapy following initial resolution of BV symptoms, and overall. For the time-to-failure analysis, time was defined as the number of days since the second visit where clinical resolution of initial BV was confirmed. The non-parametric maximum likelihood estimate (NPMLE) of the survival curve was estimated using the interval package in R to account for the interval censored data. Results are presented using an Amsel criteria score of ≥ 3 as well as ≥ 1 for BV diagnosis. All analyses were conducted using R 4.2.2 (R Core Team, 2020) in RStudio (RStudio Team 2021).

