3.1 Primary Outcome Measures To estimate the efficacy and safety of once-weekly oral secnidazole granules for suppressive therapy of recurrent BV and to qualitatively compare to previously published efficacy and safety data of multiple-dose nitroimidazole suppressive regimens for the treatment of recurrent BV to aid in the design of a larger comparative trial.

3.1.1 Efficacy: The primary efficacy endpoint is failed treatment, defined as having at least 1 episode of RBV in the 30 week follow-up period. An episode of RBV (failed treatment) will be diagnosed if the subject has a Amsel score of 3 or higher. We will report total number of RBV episodes, overall failure rate, and time to failure after initial treatment. We will also report rates of RBV if diagnosed as ≥ 1 Amsel criteria is met per FDA recommendations, but the primary outcome will be ≥ 2 criteria to be consistent with prior literature and recommendations.

3.1.2

3.1.2.1 The Amsel criteria:

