3.1.2.1.1 Thin, white, yellow, homogeneous discharge

3.1.2.1.2 Clue cells on wet mount microscopy

3.1.2.1.3 a vaginal fluid pH of over 4.5 when placing the discharge on litmus paper

3.1.2.1.4 Release of fishy odor when adding 10% potassium hydroxide (KOH) solution to wet mount - also known as “whiff test.”

3.1.3 Safety: adverse events via MedDRA criteria.

3.2 Secondary Outcome Measures Time to recurrence measured by failure rates and time-to-failure. Defined by Amsel's criteria or by Nugent criteria (gram stain results). To be measured at visit 2 (3-5 days after initial treatment), visits 3-6 (week 6, 10, 14, and 18 during suppressive treatment), visits 7 & 8 (22 & 30 weeks after initiation of treatment).

3.3 Tertiary/Exploratory/Correlative Outcome Measures Participant compliance, tolerance, and adverse event data to be collected via a patient questionnaire at each visit. The safety of secnidazole was evaluated in five Phase 1 clinical trials before FDA approval. The five most common treatment-associated adverse events were: vulvovaginal candidiasis, headache, nausea, diarrhea, abdominal pain, and vulvovaginal pruritis. We will monitor for the frequency and severity of these events and any other subject-related side effects.

4. Eligibility Criteria

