4.1 Inclusion Criteria

- Age 18 -50
- Ability to consent in English
- Current symptomatic bacterial vaginosis infection (\geq 3 Amsel criteria).
 - Amsel's criteria: Homogenous vaginal discharge, vaginal pH >4.5 , positive amine odor, and/or presence of $>20\%$ clue cells /hpf on saline mount microscopy
- History of at least 2 previous episodes of BV in the past 1 year.

Continuation after Second Visit

- Clinical resolution of bacterial vaginosis defined as: (asymptomatic and \leq 2 Amsel criteria, will also be reported as asymptomatic and \leq 1 Amsel criteria).

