4.2 Exclusion Criteria

[figure not shown]
- Current gynecologic infection or condition, including candida vaginitis, gonorrhea, chlamydia, trichomonas, desquamative inflammatory vaginitis, atrophic vaginitis.
- Pre-existing heart conditions
- Pre-existing neurological conditions
- Currently Pregnant or breastfeeding
- Women taking anticoagulants, lithium, metoclopramide, or disulfiram therapy
- Hypersensitivity to secnidazole or other drugs in the same class.

5. Study Design

A single-center prospective pilot study with once-weekly oral secnidazole granule treatment of an acute condition for two weeks followed by prophylactic treatment of asymptomatic responders with once-weekly secnidazole for 16 weeks, followed by no therapy for 12 weeks. The final follow-up evaluation is at week 30.

Eligible women with a current symptomatic bacterial vaginosis infection (\geq 3 Amsel criteria) and a history of at least 2 previous episodes of bacterial vaginosis in the past year will be enrolled in the open-label treatment study. All women will be treated with 2g of secnidazole granules orally once weekly for 2 weeks. At the second visit, 3-5 days after completion of treatment, women who have a clinical resolution of bacterial vaginosis (asymptomatic and \leq 2 Amsel criteria, will also be reported as asymptomatic and $<$ 1 Amsel criteria) will continue on once-weekly secnidazole for 16 weeks.

Patients will be evaluated at week 6, 10, 14, and 18 for recurrence of bacterial vaginosis. This will include questions about symptoms as well as a pelvic examination for assessment of vaginal discharge (\geq 3 Amsel criteria). We will also collect any information on other clinical evaluations for recurrence and the dates of diagnoses and types of treatments they may have received. Those who remain without recurrence during the 16-week suppressive phase will be followed for an additional 12 weeks off therapy, with assessment for recurrence at weeks 22 and 30. Throughout the study, data will be collected on participants' compliance and on the occurrence of adverse events.

6. Enrollment

Participants presenting to the IU Coleman Center with a history of recurrent bacterial vaginosis who are currently symptomatic will be evaluated for enrollment in the study. Informed consent will be obtained.

7. Study Procedures

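### The Amsel ≥1 suppression analysis has no stated risk set at visit 2, and two of the protocol's three resolution rules admit women who already meet the ≥1 event

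*SAP*

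**What the plan says.** SAP 1.1 gives failure rates for initial treatment, for "suppression therapy following initial resolution of BV symptoms", and overall. For the survival curve, "time was defined as the number of days since the second visit where clinical resolution of initial BV was confirmed". It then states: "Results are presented using an Amsel criteria score of ≥ 3 as well as ≥ 1 for BV diagnosis". It attaches no Amsel score to resolution and does not describe who is at risk under each threshold.

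The protocol does give scores, but not one rule. Section 4.1 (Continuation after Second Visit) has "asymptomatic and \leq 2 Amsel criteria, will also be reported as asymptomatic and \leq 1 Amsel criteria". Section 5 keeps ≤2 as the main rule but gives the additional version as "will also be reported as asymptomatic and $<$ 1 Amsel criteria", which is a score of 0.

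On the event side, section 3.1.1 says "An episode of RBV (failed treatment) will be diagnosed if the subject has a Amsel score of 3 or higher" and adds "We will also report rates of RBV if diagnosed as ≥ 1 Amsel criteria is met per FDA recommendations". Section 3.2 includes V2 among the assessment points for failure: "To be measured at visit 2 (3-5 days after initial treatment".

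**The concern.** A time-to-failure analysis needs everyone to be free of the event at time zero. If the woman who defines time zero may still have one or two Amsel criteria, and the event is one or more, she can meet the event on the day she enters. When the same finding is still there at V3, it is recorded as a failure of suppression, although nothing has recurred. The interval-censored estimator does not repair this. It handles uncertainty about when between two visits an event happened, not whether a woman was at risk at the start.

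The ≥1 suppression rate and the first step of the ≥1 curve are at stake. They are additional results, but the protocol promises the ≥1 report, and section 12 says that rates from this pilot will be used to size a larger comparative trial.

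**Working it through.** **1. The plan's own figure.** Protocol section 12: 50 women, 15% lost, 51% recurrence. 50 × (1 − 0.15) = 42.5, about 42. 42.5 × (1 − 0.51) = 20.8, about 21. The exact 95% interval for 21/42 is 0.342 to 0.658, half-width 0.158. This agrees with the stated 0.34 to 0.66 and 0.16. It is not in dispute and serves only as a scale below.

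**2. Which V2 scores are both resolved and an event?**

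| V2 resolution rule | Event ≥1 | Event ≥3 |
|---|---|---|
| ≤2 (sections 4.1 and 5, main rule) | 1, 2 | none |
| ≤1 (section 4.1, additional) | 1 | none |
| <1 (section 5, additional) | none | none |

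The overlap exists only for the ≥1 event, and only under ≤2 or ≤1.

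**3. Where it would appear.** Protocol section 8 puts V2 at day 18 and V3 at week 6 (day 42): 42 − 18 = 24 days. Taking the windows as ±1 day at V2 and ±5 days at V3, the range is (42 − 5) − (18 + 1) = 18 to (42 + 5) − (18 − 1) = 30 days. Persistence would fall in this first interval.

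**4. Size.** Let q be the share of the risk set with 1 or 2 criteria at V2, r the proportion of them who later score ≥1, and f0 that proportion among women with 0 at V2. The recorded rate is q·r + (1 − q)·f0, so the shift against the score-0 women is q(r − f0). It is upward only if r > f0.

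The documents give none of q, r and f0. The following is an illustration, assuming that all 42 women meet ≤2 at V2 and that f0 = 0.5:

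| Women at 1–2 | Later ≥1 | Score-0 women only | All 42 | Shift (points) |
|---|---|---|---|---|
| 4 | 1 of 4 | 19/38 = 50.0% | 20/42 = 47.6% | −2.4 |
| 4 | 3 of 4 | 19/38 = 50.0% | 22/42 = 52.4% | +2.4 |
| 4 | 4 of 4 | 19/38 = 50.0% | 23/42 = 54.8% | +4.8 |
| 8 | 2 of 8 | 17/34 = 50.0% | 19/42 = 45.2% | −4.8 |
| 8 | 6 of 8 | 17/34 = 50.0% | 23/42 = 54.8% | +4.8 |
| 8 | 8 of 8 | 17/34 = 50.0% | 25/42 = 59.5% | +9.5 |

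With f0 = 0.7 and r = 0.85 or 1, the same q values give +1.4 to +5.7. At an extreme, with half the women at 1–2 and all persisting, the shift is 21/42 × (1 − 0.5) = 25.0 points. With no women at 1–2 it is zero.

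**5. Overall ≥1 rate.** With residual women in the risk set it is q·r + (1 − q)·f0. If they are instead counted as initial-treatment failures it is q + (1 − q)·f0. The difference is q(1 − r), which is never negative. In the rows with three quarters later positive, the overall rate goes from 22/42 to 23/42 (+2.4 points) or from 23/42 to 25/42 (+4.8). If all persist it does not change. So the overlap does not inflate the overall ≥1 rate; it moves failures between phases or misses some.

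**The case against.** The strongest reply is that the SAP can fairly be read as already correct. Its sentence on thresholds covers BV diagnosis in general and is not limited to visits after V2. If BV is diagnosed at ≥1, a woman scoring 1 or 2 at V2 still has BV. She fails initial treatment and never enters the suppression set. The <1 wording in protocol section 5 fits this, as does the listing of V2 as an assessment point in section 3.2. This stands: the documents do not show that the analysis was done wrongly.

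It does not close the matter. Section 4.1 says ≤1, the main rule is ≤2, and the SAP describes entry by resolution of symptoms with no score. If the < in section 5 is a slip for ≤, no written resolution rule is compatible with a ≥1 event.

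A reader might also infer that the ≥1 suppression rate is biased upward. That needs two things that the documents do not supply: that ≤2 or ≤1 set the risk set, and that r exceeds f0. Persistence makes r > f0 plausible, but the shift is downward if women with residual criteria mostly clear and stay clear. The 42 in section 12 allows only for early loss and is not a count of V2 responders, and its 50% is not a ≥1 rate.

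Finally, little hangs on it. The ≥1 result is secondary to ≥3, the trial is a single-arm pilot without a hypothesis test, and with 4 to 8 residual women the shift is smaller than the planned half-width of 16 points. This limits the importance, although a confidence interval does not account for a systematic shift.

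**Conclusion.** The point holds as an unresolved conflict between the time origin and the ≥1 event, not as a demonstrated error. Two of the three written resolution rules, applied as they stand, let women into the ≥1 risk set who already meet the event. The third does not, and the SAP does not say which was used.

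Only the ≥1 suppression rate and curve are affected. A reader might extend the problem to the ≥3 result or to the overall ≥1 rate. The overlap for ≥3 is empty under every rule, and the overall ≥1 rate is not shown to be inflated. The size is unknown. The illustrated −4.8 to +9.5 points rests on assumed values for the share with residual criteria, their later rate and the rate in score-0 women.

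Section 3.1.1 also calls failure a score of 3 or higher and then sets the primary outcome at ≥2. That is a separate contradiction about the primary endpoint and does not make the present point more serious.

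**What to change.** 1. State in the SAP that the ≥1 suppression rate and curve use asymptomatic women with 0 Amsel criteria at V2. Count women scoring ≥1 at V2 as not resolved at initial treatment under ≥1. Report the number at risk at V2 for each threshold. If this was already done, one sentence saying so is enough. If not, label it post hoc, since the SAP is written in the past tense, and show the original ≥1 result beside it.
2. Reconcile ≤1 (protocol 4.1) with <1 (protocol 5) for analysis reporting.
3. Separately, reconcile the two failure thresholds in protocol 3.1.1 with each other and with the SAP, which has no ≥2 analysis. Under ≥2, a woman with 2 criteria at V2 would be both resolved under ≤2 and failed.

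A sensitivity analysis that keeps women with residual criteria and counts an event only after a visit with 0 criteria is not advised. A woman scoring 1, then 2, then 4 fails at ≥3 but would be no event at ≥1.

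The work is SAP wording and, if needed, a re-run on V2 data already collected. Costs to disclose:

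- The ≥1 risk set shrinks. At a 50% rate the exact half-width goes from 0.158 (n = 42) to 0.166 (n = 38) or 0.176 (n = 34).
- The ≥1 and ≥3 suppression rates have different denominators.
- Some women who received suppression leave the ≥1 suppression set.
- The ≥1 initial-treatment failure rate rises, by 4/42 = 9.5 or 8/42 = 19.0 points in the illustration, and the overall ≥1 rate may rise by q(1 − r).

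These changes concern analysis sets only. Which resolution rule governs continuation of treatment is not judged here.

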Secnidazole is a nitroimidazole antimicrobial indicated for the treatment of bacterial vaginosis in adult women with a much longer half-life than both metronidazole and tinidazole. While suppressive therapy can be curative or can increase symptom free intervals, patient compliance with complicated and prolonged treatment regimens are barriers to successful outcomes. Compared to metronidazole and tinidazole, secnidazole has a much longer half-life (metronidazole and tinidazole: 8 hours and 12-14 hours vs. secnidazole: 17-29 hours).

To date, there are no studies that have evaluated secnidazole for suppressive therapy of recurrent BV. In a randomized double-blind trial, clinical cure and/or symptom improvement rates were similar in women with bacterial vaginosis treated with a single dose of secnidazole (90.8%) or tinidazole (87.5%). Data from two non-blinded studies indicated that a single dose of secnidazole was at least as effective as 7-day treatment with metronidazole (secnidazole 73.3 to 93.1%; metronidazole 58.5 to 95.8%).³

From this data, it is reasonable to speculate that once weekly dosing of secnidazole for suppressive therapy of recurrent BV may be at least as effective as the current more complex therapies and would be a valuable treatment alternative to women suffering with recurrent BV due to the more simplified dosing regimen.

Simplifying suppressive protocols could improve patient compliance and decrease the recurrence of disease. Poor adherence increases with longer durations of treatment and studies of compliance rates show that 50% of women do not adhere to 5-7 day treatments for BV.^{4,5} Poor adherence leads to treatment failures and recurring infections and increases the potential for resistant organisms.⁶ Utilizing a drug such as secnidazole, which has a much longer half-life may provide an improved therapeutic window for suppression of causative microorganisms and could prevent a recurrence.

2. Objectives

2.1 Primary Objective. To determine the efficacy and safety of once-weekly oral secnidazole granules for suppressive therapy of recurrent BV to previously published efficacy and safety data of multiple-dose nitroimidazole suppressive regimens for the treatment of recurrent BV.

2.2 Secondary Objective. To determine the meantime to recurrence of BV after treatment.

2.3 Tertiary/Exploratory/Correlative Objectives. To evaluate participant compliance, tolerance, and occurrence of adverse events.

3. Outcome Measures/Endpoints

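### The only time-to-failure curve is conditional on resolution at Visit 2, so it overstates the failure-free share of all women assessed

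*SAP*

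**What the plan says.** Protocol Section 3.1.1 defines the primary endpoint as "failed treatment, defined as having at least 1 episode of RBV in the 30 week follow-up period", with this threshold: "An episode of RBV (failed treatment) will be diagnosed if the subject has a Amsel score of 3 or higher". It makes no exception for an Amsel score of 3 or more at Visit 2. It then commits to three summaries: "We will report total number of RBV episodes, overall failure rate, and time to failure after initial treatment".

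Protocol Section 3.2 covers failure rates and time to failure, and Visit 2 heads its list of measurement times: "To be measured at visit 2 (3-5 days after initial treatment), visits 3-6 (week 6, 10, 14, and 18 during suppressive treatment". The off-treatment visits follow.

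Protocol Sections 4.1 and 5 also make Visit 2 a gate. Only women who are asymptomatic with at most 2 Amsel criteria go on to the 16-week suppressive phase.

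SAP Section 1.1 estimates failure rates with exact 95% intervals for initial treatment, for suppression after resolution, and overall. For the time-to-failure analysis it says "time was defined as the number of days since the second visit where clinical resolution of initial BV was confirmed", and it fits an NPMLE for interval-censored data. It describes no other curve.

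**The concern.** Visit 2 is an outcome visit in the protocol and an entry condition in the SAP. A woman without confirmed resolution at Visit 2 is neither in the risk set nor an event on the SAP curve. The curve therefore describes responders, while the protocol's time to failure has no such restriction.

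Two things are at stake. First, the report will show an overall failure rate beside a curve that ends at a lower value. Both are called failure, and the SAP does not explain why they differ. Second, Protocol Section 12 says the pilot's rates will feed the sample-size calculation for a larger comparative trial. Anyone who reads the curve as time to failure in all treated women would plan with too low a week-30 event proportion.

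**Working it through.** **The plan's own figure.** Section 12 expects 15% early loss from 50 women and 51% recurrence by the end of follow-up. That gives 50 × 0.85 = 42.5, and 42.5 × 0.49 = 20.8, about 21. The exact 95% interval for 21/42 is 0.342 to 0.658, half-width 0.158, so the stated 0.34 to 0.66 reproduces. This figure makes no allowance for Visit 2 failures and does not depend on the time origin, so it does not test the point.

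**Inputs.**
- Recurrence of 25.5% at the end of maintenance and 51% at the end of follow-up (Section 12). I assume these apply to women resolved at Visit 2, with a constant hazard within each phase.
- Visit 2 at Day 18 (Section 8). Week 18 (Day 126) is then 108 days later and week 30 (Day 210) is 192 days later.
- f, the share failing at Visit 2, is not given for two doses. The background section cites single-dose response of 73.3% to 93.1% in two non-blinded studies and 90.8% in a blinded trial. I take f = 1 − response: 6.9%, 9.2% and 26.7%. Of 42 women, these are about 3, 4 and 11.

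**Failure-free share.** Let S(t) be the SAP curve at t days after Visit 2. Among all women assessed at Visit 2, the share still failure-free is (1 − f) × S(t). The SAP curve is too high for that group by 1/(1 − f): 1/0.931 = 1.07 at the low end and 1/0.733 = 1.36 at the high end. Only this step is free of assumptions about the shape of the curve.

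Week-30 failure, 1 − (1 − f) × 0.49:
- f = 6.9%: 1 − 0.931 × 0.49 = 54.4%
- f = 9.2%: 1 − 0.908 × 0.49 = 55.5%
- f = 26.7%: 1 − 0.733 × 0.49 = 64.1%

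The SAP curve would show 51% in each case.

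**Median.** The daily hazards are h1 = −ln(0.745)/108 = 0.00273 and h2 = ln(0.745/0.49)/84 = 0.00499. The SAP median is 108 + ln(0.745/0.5)/h2 = 188 days after Visit 2. The all-assessed median solves (1 − f) × S(t) = 0.5. A Day 1 origin adds 17 days. An origin at the end of the two-week course (about Day 14) adds about 4.

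| f | From Visit 2 | From about Day 14 | From Day 1 | SAP curve |
|---|---|---|---|---|
| 6.9% | 174 | 178 | 191 | 188 |
| 9.2% | 169 | 173 | 186 | 188 |
| 26.7% | 126 | 130 | 143 | 188 |

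On a Day 1 clock the two medians are equal at f = 1 − exp(−17 × h2), about 8%. On an end-of-course clock they are equal at f = 1 − exp(−4 × h2), about 2%.

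**The case against.** A reader might infer that the SAP makes time to failure look longer. The documents do not support that as a general statement. Dropping Visit 2 failures lengthens the median, but starting the clock later shortens every included time. On a Day 1 clock the all-assessed median is the longer one when f is below about 8%, which lies inside the assumed range.

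A reader might also infer that the two clocks differ by the full 17 days. Section 3.2 uses the same phrase for a point just before Visit 2, "To be measured at visit 2 (3-5 days after initial treatment", and dates the last two visits from the initiation of treatment instead. On that reading the protocol's origin is only 3 to 5 days before the SAP's, and the main difference is the population.

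The SAP's population is also defensible. The secondary objective is "To determine the meantime to recurrence of BV after treatment", and recurrence presupposes resolution. Every woman enters with at least 3 Amsel criteria, so an event by Visit 2 is persistence rather than recurrence. The benchmark, with 16 weeks of maintenance inside a 28-week total, also appears to run from the start of maintenance.

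Nor are Visit 2 failures hidden. The SAP states its origin plainly and reports initial-treatment and overall failure rates.

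The size is soft as well. The f values come from single-dose studies, and the 90.8% includes symptom improvement, so its complement is not the share with an Amsel score of 3 or more. The gap of 3 to 13 points lies within the protocol's half-width of 16 points, in a single-arm descriptive pilot.

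All of this stands, and it limits the point without removing it. Section 3.2 still lists Visit 2 as a time-to-failure visit. The overall rate is a simple proportion with an exact interval, which handles neither loss to follow-up nor the visit intervals. No planned analysis gives the protocol's time to failure without conditioning on response.

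**Conclusion.** The mismatch is real and should be corrected, but it is one of population and labelling. It does not invalidate the suppression-phase curve, which is a legitimate summary of recurrence during and after suppression.

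For any f above zero, the SAP curve overstates the failure-free share of all women assessed by 1/(1 − f) at any given time after Visit 2. With f between 6.9% and 26.7% and 51% recurrence among responders, week-30 failure is about 54% to 64% rather than 51%. That range rests on borrowed single-dose response rates and on treating every woman unresolved at Visit 2 as a failure. No direction can be claimed for the median until f is known and the origin is fixed.

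**What to change.** In SAP Section 1.1:
1. Keep the current curve and label it *time to recurrence, conditional on resolution at Visit 2*.
2. Add one NPMLE curve of time to treatment failure in all treated women, with failure at Visit 2 entered as an event interval-censored up to Visit 2.
3. State one origin for time after initial treatment: the start or the end of the initial course.
4. State how women are handled who are symptomatic at Visit 2 with at most 2 criteria. For the analysis at 1 or more criteria, do the same for women who count as resolved but already meet that threshold at time zero.

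In Protocol Section 3.2, make Visit 2 an outcome visit for the all-treated curve and the time origin for the conditional curve.

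The cost is some wording and one more fit on data already collected. The downside is that the all-treated curve will show a less favourable failure-free share than the responder-only curve.
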